9.4.2 Secondary Endpoints Analyses

1. Technical success: The number and percentage of lesions achieving technical success will be summarized and an exact 95% confidence interval will be provided. Analysis will be conducted using FAS and PP analysis sets. Technical success is captured on the “Ablation Outcome” form on eCRF. Technical success is achieved when the treating physician choose the response as “complete ablation” for the question “Per treating physician, what was the outcome of the ablation?”. The summary statistics will also be presented for per patient. The technical success is considered achieved at a patient-level when all treated lesions for a patient were successful.

2. Technique efficacy: The number and percentage of lesions achieving technique efficacy will be summarized and an exact 95% confidence interval will be provided. Analysis will be conducted using FAS and PP analysis sets. Technique efficacy is captured on the eCRF based on the response as “yes” from the physician performing ablation for the question “Was technique efficacy achieved for target lesion?” from the “Technique Efficacy” form. The summary statistics will also be presented for per patient. The technique efficacy is considered achieved at patient-level when all treated lesions for a patient were successful.

3. Hospital resources utilization: Summary of endpoints related to hospital resources utilization will include number of patients (N), mean, standard deviation, median, minimum, and maximum and will be based on FAS. Following endpoints will be presented on the summary tables:

a) Length of post-ablation hospital stay. Length of post-ablation hospital stay will be derived from the Discharge and Ablation forms on eCRF. It will be derived as

Length of post-ablation hospital stay = (date and time of hospital discharge – date and time of ablation ended).

b) Time to perform procedure, which includes 3 measures of time:

i) Overall procedure duration, defined as the time elapsed between loading CT dataset into the AC system and completion of MWA with last probe removal. The overall procedure duration is captured on the Ablation Procedure form on eCRF.

ii) AC imaging duration, defined as the time elapsed between loading CT dataset into AC to plan for the target ablation and last use of AC to plan for the final ablation. AC imaging duration is captured on the Ablation Procedure form on eCRF.

iii) Ablation duration, defined as the time elapsed between ablation first probe puncture and removal of the last probe at the completion of the ablation. Ablation duration is captured on the Ablations form on eCRF under the variable name “Duration.”

Other endpoints associated with hospital resources utilization will be listed.

4. Device-related and procedure-related AEs and all SAEs from the time of the first probe puncture (Visit 2) through study completion (Visit 3 or early termination from the study) will be summarized based on FAS. Further details on safety analysis are presented on Section 9.5.

5. Device User Experience questionnaire: It is measured by the “Ablation Confirmation User Evaluation Questionnaire” and completed by the performing physician. The first half will be completed following each ablation procedure and the second half will be completed approximately every 5 ablations (per treating physician). The questionnaire will be summarized by its items for the frequencies and corresponding percentages based on the FAS. A listing will be provided for the Ablation Confirmation User Evaluation Questionnaire.

6. Patient Quality of Life questionnaires: Quality of Life will be measured using EORTC QLQ-C30 and liver specific QLQ-HCC18 at Visit 2 (pre-ablation) and Visit 3.

C30 and HCC18 overall scores will be derived to have an overall representation of all domains/items in QLQ-C30 and QLQ-HCC18, respectively. The scores for C30 and HCC18 will be derived as per the guidance on the European Organization for Research and Treatment of Cancer (EORTC) QLQ-C30 scoring manual version 3.0.

The overall scores for each scale and the changes from Visit 2 to Visit 3 will be summarized using N, mean, standard deviation, minimum, maximum, and median based on the FAS. The overall scores for each scale will be listed.

EORTC QLQ-C30:

The EORTC QLQ-C30 (version 3.0) comprises 30 questions and provides a multi-dimensional assessment of QoL.

The QLQ-C30 is composed of both multi-item scales and single-item measures. EORTC QLQ-C30 can be combined to produce 5 functional scales (Physical, Role, Cognitive, Emotional, Social), 3 symptom scales (Fatigue, Pain, Nausea/vomiting), 5 individual items (dyspnea, insomnia, appetite loss, constipation, diarrhea) and a global measure of health status.

Each of the multi-item scales includes a different set of items - no item occurs in more than one scale. All the scales and single-item measures range in score from 0 to 100. A high scale score represents a higher response level.

There are four responses for each question from Q1 to Q28: from not at all, a little, quite a bit, to very much, each will be scored from 1 (not at all) to 4 (very much). For Q29 and Q30, scores will be from 1 (very poor) to 7 (Excellent).

No response (NR) means no response to any of the questions and will be considered as missing as well as not included in the analysis.

Table 1: Scoring the EORTC QLQ-C30 version 3.0

Scale	Number of items	Item range*	Item numbers
Global health status /			
Global health status/QoL	2	6	29, 30
Functional scales			
Physical functioning	5	3	1 to 5
Role functioning	2	3	6, 7
Emotional functioning	4	3	21 to 24
Cognitive functioning	2	3	20, 25
Social functioning	2	3	26, 27
Symptom scales / items			
Fatigue	3	3	10, 12, 18
Nausea and vomiting	2	3	14, 15
Pain	2	3	9, 19
Dyspnoea	1	3	8
Insomnia	1	3	11
Appetite loss	1	3	13
Constipation	1	3	16
Diarrhoea	1	3	17
Financial difficulties	1	3	28

* Item range is the difference between the possible maximum and the minimum response to individual items; most items take values from 1 to 4, giving range = 3.

The scoring procedures is as follows:

For each of the 15 scales/items in Table 5, a score is computed by taking the following steps:

For scales with more than one item, raw scores (RS) are the sum of scores for each item divided by number of items:

$$RS = (Q1 + \dots + Qn) / n, \text{ where } n \text{ represents the number of non-missing item scores}$$

If at least half of the component items from the scale have been answered, the raw score will be calculated as the average of the non-missing items, otherwise the raw score will be set to missing. This is equivalent to the raw score being taken as the mean of the non-missing item values.

For single item scales, the raw score is simply the score for that item. If a single-item score is missing, the single-item scale raw score is missing.

Scale scores (S) are calculated by a linear transformation to 0-100:

For Functional scales:

$$Score = S = \left(1 - \frac{RS-1}{Range}\right) \times 100$$

For Symptom scales / items and Global health status / QoL:

$$Score = S = \left(\frac{RS-1}{Range}\right) \times 100$$

Range is the difference between the maximum possible value of RS and the minimum possible value. The EORTC QLQ-C30 has been designed so that all items in any scale have the same range. Therefore, the range of RS equals the range of the item values. Most items are scored 1 to 4, giving range = 3. The exceptions are the items contributing to the global health status / QoL, which are 7-point questions with range = 6.

All the scales and single-item measures are linearly transformed so that each score ranges from 0 to 100. Higher scores for the global health status/ QoL scale and functioning scales indicate a higher/healthier level of functioning and a higher/better QoL respectively, whereas higher scores in symptom scales represent a higher level of symptoms/problems.

Example:

Emotional functioning (EF):

$$Raw score (RS) = (Q21 + Q22 + Q23 + Q24)/4$$

$$EF score = \{1 - ((RS - 1)/3)\} * 100$$

The EORTC QLQ-C30 Summary Score is calculated from the mean of 13 of the 15 QLQ-C30 scales (the Global Quality of Life scale and the Financial Difficulties scale are not included). Prior to calculating the mean, the symptom scale/individual item scale scores need to be reversed (i.e., 100 minus the scale score) to obtain a uniform direction of all scales. The summary score will only be calculated if all the required 13 scale scores are available (using scale scores based on the completed items, provided that at least 50% of the items in that scale have been completed).

EORTC QLQ-HCC18:

EORTC QLQ-HCC18 includes 18 multi-item scales. These items are grouped into 6 domains (fatigue, body image, jaundice, nutrition, pain and fever). Two remaining single items address abdominal swelling and sex life. All scales will be grouped and converted to scores of 0 to 100 according to the scoring manual; a higher score represents a more severe symptom or problem.

Table 2: Scoring the EORTC QLQ-HCC18

Scale	Number of items	Item range*	Item numbers
Symptom scales / items			
Fatigue	3	3	15, 16, 17
Body Image	2	3	3, 5
Jaundice	2	3	6, 7
Nutrition	5	3	1, 2, 12, 13, 14
Pain	2	3	8, 9
Fever	2	3	10, 11
Abdominal Swelling	1	3	4
Sex life	1	3	18

* *Item range* is the difference between the possible maximum and the minimum response to individual items; most items take values from 1 to 4, giving *range* = 3.

The scoring procedures as below:

For each of these domains, a symptom score is computed by taking the following steps:

- (1) sum across the item responses on that domain,
- (2) divide by the number of non-missing items to obtain the mean of item response (RS),
- (3) subtract 1 from the mean of the item responses (i.e., item response means – 1),
- (4) divide by the number in Item Range
- (5) multiply by 100.

This results in symptom scores that range from 0 to 100 with higher scores indicating greater symptom severity. These symptom scores can be computed if at least 50% of the items have responses (i.e., 1 item response needed for 1 item domains, 1 item response needed for 2 item domains, 2 item responses needed for 3 item domains).

HCC18 index-score is defined as the sum of all 8 QLQ-HCC18 symptom/problem scales divided by 8 (the total number of QLQ-HCC18 scales). A higher HCC18 index-score reflects a worse overall Health-related quality-of-life (HRQOL).

7. Pain scores collected through the Patient Numeric Pain rating Scale (NPRS) questionnaire at Visit 2 (pre- and post-ablation) and Visit 3 will be summarized as a continuous variable. The changes in pain score from Visit 2 (pre-ablation) to Visit 2 (post-ablation) (Visit 2 Pre-ablation – Visit 2 Post-ablation) and from Visit 2 (pre-ablation) to Visit 3 (Visit 2 Pre-ablation – Visit 3) will also be presented.

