10.9 Analyses to be Conducted

Categorical variables will be summarized descriptively by frequencies and associated percentages. Continuous variables will be summarized descriptively by number of patients, mean, standard deviation, median, minimum, and maximum. Confidence intervals will also be provided for procedure-related variables.

Disposition of Study Patients

Patient disposition will be summarized using counts and percentages. The number and percentage of patients completed and discontinued along with the specific reasons for discontinuation will be tabulated by treatment group and in total.

Demographic and Baseline Characteristics

Summary statistics will be provided for patient demographics and pre-operative ablation characteristics.

Primary and Secondary Endpoint(s) Analyses

The number and percentage of patients requiring probe replacement/changes using the AC software prior to the initial ablation will be summarized and a 95% confidence interval for the percentage will be provided. The number and percentage of patients in whom the AC software indicates repeat ablation is indicated based on insufficient margins following the initial ablation procedure will be summarized in a similar manner.

The number and percentage of patients achieving technical success will be summarized and a 95% confidence interval will be provided. A similar summary will be provided for

technique efficacy.

The number and percentage of patients experiencing device-related and procedure-related AEs and all SAEs from the time of the first probe puncture (Visit 2) through study completion, or, if applicable, the day of early withdrawal, will be summarized by MedDRA preferred term and system organ class. Ninety-five percent confidence intervals may be provided for pre-specified adverse events of interest. The expected side effects related to MWA are as follows:

- Ascites (accumulation of fluid causing abdominal swelling)
- Biloma / bile leak (buildup of the bile within the abdomen / bile leak)
- Bile duct injury
- Bleeding requiring transfusion, embolization, or prolonged hospital stay
- Intrahepatic hematoma
- Pneumothorax or hemothorax
- Organ injury other than the liver (such as gastrointestinal injury/perforation or diaphragmatic injury/hernia)
- Fever
- General feeling of tiredness
- Infection
- Liver dysfunction
- Liver abscess
- Nausea
- Pain
- Pneumonia
- Pleural effusion

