1.2 Study Design

This was a prospective, single-arm, multicenter clinical study that generated clinical data using NEUWAVE Microwave Ablation System with Ablation Confirmation Software in patients undergoing MWA of at least one soft-tissue liver lesion as part of the study site's SOC treatment.

2 Treatment Assignment

This was a single-arm study where all enrolled patients were ablated using the NEUWAVE Microwave Ablation System and the AC software tool.

3 Randomization and Blinding Procedures

This is a single-arm, open-label study. No randomization occurred and no blinding procedures were required.

4 Interval Windows

Interval windows are not defined for the purpose of analysis in this study outside of the visit windows that are provided in the Schedule of Assessments in Table 1 of the final protocol. There will be no assigning of observations to time points outside of the visit to which they are recorded in the electronic Case Report Forms (eCRFs). Data collected in Unscheduled Visit forms will be listed as such.

5 Level of Significance

No hypotheses are specified for this study and no p-values are being calculated. Therefore, no level of significance is specified. For selected endpoints 95% confidence intervals will be estimated.

6 Analysis Sets

The study protocol identified two analysis sets:

- The Full Analysis Set (FAS) will consist of all eligible patients who are enrolled in the study and had the ablation procedure attempted with the AC tool. Lesions from patients in FAS that had the ablation procedure attempted with the AC tool will be included on the FAS. The FAS will be the primary analysis set for safety and effectiveness endpoints. Patients followed by lesions for whom the response was "Yes" to the question "Was

ablation confirmation software used to validate probe placement?” on the Ablation Confirmation form on the eCRF will be included on the FAS.

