9.1 General Conventions

Patient data will be summarized using listings and tables. All eCRF data will be listed per patient for all patients. Descriptive statistical analyses will be provided for pre-specified study endpoints. Summaries for continuous variables will include number of observations (n), mean, standard deviation, median, minimum, and maximum. Summaries for categorical variables will include number and percentage.

Analyses will be conducted using SAS software version 9.4 or higher. During the course of analysis programming of tables that are mocked up in this SAP, minor modifications may become necessary. Examples of these minor modifications include, but are not limited to, rewording of a footnote, addition of a footnote, re-labeling of a column, or addition or removal of a column from a listing. In cases where modifications to tables or listings are not related to a change in statistical analysis methodology or conclusions that could be made on the originally proposed methodology, then no amendment of the SAP is necessary. Any final analyses that

differ from what has been specified in this document will be identified within the final statistical output and documented within the clinical study report.

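### The exact 95% intervals for the lesion-level technical success and technique efficacy percentages treat a patient's lesions as independent, so they can be too narrow if multi-lesion patients are common and their outcomes correlated.

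*SAP*

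**What the plan says.** SAP 9.4.2 makes the lesion the unit for both endpoints. On the first of them it reads: "The number and percentage of lesions achieving technical success will be summarized and an exact 95% confidence interval will be provided". The second is handled in the same way: "The number and percentage of lesions achieving technique efficacy will be summarized and an exact 95% confidence interval will be provided". Both are planned for the full analysis set and the per-protocol set. Section 9.4.2 does not name the exact method. SAP 9.4.1 names Clopper-Pearson for the repositioning endpoint. Nothing in the SAP deals with correlation between lesions of one patient, and protocol 6.1 allows up to three lesions to be ablated in a procedure.

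For patients, SAP 9.4.2 adds "The summary statistics will also be presented for per patient". It counts a patient as a success only if every lesion treated in that patient succeeded, and this rule is the same for both endpoints.

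Protocol 10.9 works at patient level: "The number and percentage of patients achieving technical success will be summarized and a 95% confidence interval will be provided". It asks for the corresponding patient-level summary of technique efficacy. It does not name an interval method.

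**The concern.** A Clopper-Pearson interval is exact when the observations are independent with a common success probability. Lesions treated in the same patient share the liver, the session, the imaging and the performing physician, who also judges the outcome. Positive correlation is therefore plausible, and three correlated lesions carry less information than three independent ones. The plain interval ignores this and can cover the true percentage less often than 95%.

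At patient level the problem does not arise, because each patient contributes one yes/no result. What is at stake is the precision reported for the lesion-level percentages. The point estimates are unaffected, and no hypothesis or decision rule depends on them.

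**Working it through.** **The plan's own precision figure.** Neither document states a precision for these two endpoints. The only figure is for the repositioning rate (protocol 10.8, SAP 7): 15% with 100 patients, half-width below 7%. The normal approximation gives 1.96 × √(0.15 × 0.85 / 100) = 6.998 points, so the figure reproduces. It counts patients and says nothing about lesions.

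**Inputs.** From the documents: 1 to 3 lesions per patient, an exact 95% interval, 100 patients planned, and fewer enrolled than planned (SAP 7, number not given). Assumed: lesion success 80%, 90% and 95%; 100 or 50 patients; ICC 0, 0.1, 0.3 and 0.5; and two mixes of patients with 1/2/3 lesions, 75/20/5% and 50/30/20%.

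**Expected size by formula.** With m lesions per patient, the variance of the lesion percentage is inflated by about 1 + ICC × (E[m²]/E[m] − 1).

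- 75/20/5: E[m] = 0.75 + 0.40 + 0.15 = 1.30 and E[m²] = 0.75 + 0.80 + 0.45 = 2.00, so the factor is 1 + 0.538 × ICC. At ICC 0.5 this is 1.269, and the standard error is √1.269 = 1.13 times the independence value.
- 50/30/20: E[m] = 0.50 + 0.60 + 0.60 = 1.70 and E[m²] = 0.50 + 1.20 + 1.80 = 3.50, so the factor is 1 + 1.059 × ICC. At ICC 0.3 it is 1.318 (standard error × 1.15), and at ICC 0.5 it is 1.529 (× 1.24).

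**Coverage of the plain exact interval by simulation.** Lesions were drawn as beta-binomial within patients, with 20,000 runs per cell. Ranges are over the three success rates, and the Monte Carlo standard error is about 0.15-0.2 points.

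| Patients | Mix 1/2/3 (%) | ICC 0.1 | ICC 0.3 | ICC 0.5 |
|---|---|---|---|---|
| 100 | 75/20/5 | 95.6-96.8% | 94.1-96.0% | 93.2-95.3% |
| 100 | 50/30/20 | 95.0-96.0% | 92.5-93.8% | 90.2-92.1% |
| 50 | 75/20/5 | 96.2-98.2% | 95.1-97.6% | 93.9-96.9% |
| 50 | 50/30/20 | 95.3-96.3% | 93.0-94.3% | 90.6-92.4% |

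At ICC 0, coverage is 96.1-97.2% with 100 patients and 96.2-98.4% with 50. The exact interval is conservative to begin with, and that margin absorbs weak correlation. Having fewer patients did not make matters worse.

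**Coverage of the adjusted interval.** Let patient i of K have xᵢ successes in mᵢ lesions, with n = Σmᵢ and p = Σxᵢ/n.

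1. Cluster variance: v = [K/(K − 1)] × Σ(xᵢ − p·mᵢ)² / n².
2. Effective sample size: p(1 − p)/v, multiplied by the squared ratio of the 97.5% t quantiles on n − 1 and K − 1 degrees of freedom, and capped at n.
3. Clopper-Pearson limits computed at that effective size. If v = 0, use n.

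Coverage was 95.3-98.6% over all cells. All lesions succeeded in up to about 5% of runs (50 patients, 95% success, mix 75/20/5, ICC 0.5). In those runs v = 0 and the fallback is needed.

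**Patient level for comparison.** The ordinary exact interval on patients covered 94.9-99.0% without adjustment. At 90% lesion success and ICC 0, expected patient-level success is 0.75 × 0.90 + 0.20 × 0.81 + 0.05 × 0.729 = 87.3% for 75/20/5, and 0.50 × 0.90 + 0.30 × 0.81 + 0.20 × 0.729 = 83.9% for 50/30/20. The two percentages are different quantities.

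**The case against.** The strongest objection is that the loss is hypothetical. Of the 16 combinations of patient number, mix and ICC, the lowest coverage is at least 95.0% in 9 and at least 93.0% in 13. A shortfall of 3-5 points needs half the patients to have several lesions and an ICC of 0.5, and no section of either document supports either figure. This stands and limits the point to a cheap improvement.

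A second objection is that SAP 9.4.1 uses the same kind of lesion-level interval for the primary endpoints, so changing only the secondary endpoints would be inconsistent. That also stands, and the fix covers both.

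Stronger readings are tempting, but the documents do not support them:

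- A reader might infer that the SAP drops the patient-level interval the protocol promises. The per-patient sentence follows directly on number, percentage and exact interval, and is naturally read as repeating all three. SAP 9.1 ("Summaries for categorical variables will include number and percentage") says what summaries contain without ruling an interval out, and the lesion percentages come under the same convention yet get one. SAP 5 ("For selected endpoints 95% confidence intervals will be estimated") is neutral, since both endpoints already have an interval. Protocol 10.1 describes the SAP as supplementing the protocol. Only the more explicit patient-level wording in SAP 9.4.1 leaves any doubt. This is an ambiguity and not a conflict.
- A reader might infer that the protocol promises an exact interval. It promises a 95% interval without naming a method.
- A reader might infer that patient-level success must be the lower figure. It is lower in expectation if the chance of success does not depend on the number of lesions, but it need not be in the data. If 99 patients each have one success and one patient has three failures, lesions give 99/102 = 97.1% and patients 99/100 = 99.0%.

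**Conclusion.** The point holds as a modest one. The planned lesion-level intervals assume independence between a patient's lesions and can understate uncertainty. Under the assumptions above there is essentially no loss at ICC 0.1 or lower. Coverage is about 93-97% at ICC 0.5 with mix 75/20/5, about 92-94% at ICC 0.3 with mix 50/30/20, and 90-93% at ICC 0.5 with that mix. With one lesion per patient nothing is lost. Because the lesion mix, ICC, success rate and final patient number are not given, the documents cannot show which case applies. The endpoints are secondary and descriptive, so only stated precision is affected. The per-patient interval needs no more than a clarifying sentence.

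**What to change.** 1. In SAP 9.4.2, specify a cluster-adjusted Clopper-Pearson 95% interval, with patient as the cluster, for the lesion-level percentages of technical success and technique efficacy. Revert to the plain exact interval when all lesions succeed.
2. For consistency, do the same for the lesion-level intervals in SAP 9.4.1, or label them as ignoring within-patient correlation.
3. As a clarification, state in SAP 9.4.2 that the per-patient summary of each endpoint includes an exact 95% interval. This matches the wording of SAP 9.4.1 and meets protocol 10.9.

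The cost is a sentence per endpoint and a few lines of code, and point estimates do not change. The adjusted interval is about 1.5-4% wider at ICC 0, 13-14% wider at ICC 0.5 with mix 75/20/5, and about 25% wider at ICC 0.5 with mix 50/30/20. It is somewhat conservative.
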